10.8. Appendix 8: Values of Potential Clinical Importance

10.8.1. Laboratory Values

Chemistry Values of Potential Clinical Concern

ANALYTE	Age	Sex	SI Units	F3 low	F3 high
SODIUM	0+	Both	MMOL/L	120	160
POTASSIUM	3+	Both	MMOL/L	2.8	6.5
CALCIUM	3+	Both	MMOL/L	1.50	3.24
PHOSPHORUS, INORG	3+	Both	MMOL/L	0.32	
GLUCOSE	1+	Both	MMOL/L	2.2	27.8
ALT (SGPT)	3-12	Both	U/L		>143 (and Total Bilirubin > 43)
ALT (SGPT)	13+	Both	U/L		>239 (and Total Bilirubin > 43)

Haematology Values of Potential Clinical Concern

ANALYTE	Age	Sex	SI Units	F3 low	F3 high
HAEMOGLOBIN	12+	Both	G/L	71	199
HAEMATOCRIT	12+	Both	1	0.201	0.599
PLATELET COUNT	1+	Both	GL/L	31	1499
WHITE CELL COUNT	12+	Both	GL/L	1.1	

10.9. Appendix 9: Multicenter Studies

10.9.1. Methods for Handling Centres

- In this multicentre global study, enrolment will be presented pooled across investigative sites and countries.
- For the purposes of covariate adjustment in the statistical analysis centres will be grouped into regions. The following regions are defined with consideration for standard of care medical practice, number of subjects enrolled and regulatory considerations:

Region	Countries
European Union	Belgium, France, Germany, Netherlands, Spain, Sweden
Rest of World	Argentina, Canada, United States

10.10. Appendix 10: Examination of Covariates and Subgroups

10.10.1. Handling of Covariates

- The following is a list of covariates that will be used in all model-based statistical analyses.

Category	Subgroups
Region	Europe, Rest of World (See Section 10.9 for further details)
Exacerbations in the year prior to study (to be included as an ordinal variable)	2,3,4+
Use of baseline maintenance oral corticosteroids	OCS use, no OCS use

- Additional covariates of clinical interest may also be considered.
- If the percentage of subjects is small within a particular subgroup, then the subgroup categories may be refined prior to database freeze.
- If the category cannot be refined further, then descriptive rather than statistical comparisons may be performed for the particular subgroup.

10.10.2. Handling of Subgroups

The following subgroups are of interest within this study. A separate exploratory analysis of the primary endpoint within each subgroup will be carried out.

Subgroup categories may be further collapsed if there are a small number of subjects in a treatment arm within a subgroup leading to model convergence issues.

The following subgroups are of interest for the primary efficacy endpoint:

- Exacerbations in previous year: ≤ 2 , 3, 4+ exacerbations
- Baseline blood eosinophils: < 150 , $\geq 150 - < 300$, $\geq 300 - < 500$, ≥ 500 cells/ μ l

10.11. Appendix 11: Model Checking and Diagnostics for Statistical Analyses

10.11.1. Statistical Analysis Assumptions

Endpoint(s)	
 • Mean change from baseline in ACQ-5 score at Week 32 • Mean change from baseline in SGRQ at Week 32 • Ratio to baseline in blood eosinophil count at Week 32 • Mean change Pre- and Post- bronchodilator FEV1 at Week 32
Analysis	
 • Mixed Model Repeated Measures (MMRM) 
 • In the event that this model fails to converge, the list of covariates may be adjusted and/or reduced. • If there are any important departures from the distributional assumptions, transformations of covariates may be considered or alternative models may be explored as supporting analysis.

Endpoint(s)	
 • Frequency of clinically significant asthma exacerbations over 32 week treatment • Frequency of exacerbations requiring ED visit/hospitalization during the 32 week treatment period • Frequency of exacerbations requiring hospitalization during the 32 week treatment period
Analysis	
 • Negative binomial regression analysis 
 • In the event that this model fails to converge, the list of covariates may be adjusted and/or reduced. • Distributional assumptions underlying the model used for analysis will be examined by: 
 ○ assessing if a sufficient number of events occurred within covariate categories. • If there are any important departures from the distributional assumptions, transformations of covariates may be considered or alternative models may be explored as supporting analysis.

10.12. Appendix 12: Abbreviations & Trade Marks

10.12.1. Abbreviations

Abbreviation	Description
ACQ	Asthma Control Questionnaire
ADA	Anti-drug Antibody
ADaM	Analysis Data Model
AE	Adverse Event
AESI	Adverse Event of Special Interest
AIC	Akaike's Information Criteria
ALT	Alanine Transaminase
ASE	All Subjects Enrolled
ATC	Anatomical Therapeutic Chemical
BLQ	Below Limit of Quantification
BMI	Body Mass Index
CDISC	Clinical Data Interchange Standards Consortium
CI	Confidence Interval
CIL	Clinical Investigation Leader
CPMS	Clinical Pharmacology Modelling & Simulation
CS	Corticosteroid
CSR	Clinical Study Report
DBF	Database Freeze
DBR	Database Release
DOB	Date of Birth
DP	Decimal Places
ECG	Electrocardiogram
eCRF	Electronic Case Record Form
ED	Emergency Department
EW	Early Withdrawal
FEV ₁	Forced expiratory volume in 1 second
FVC	Forced Vital Capacity
GCSP	Global Clinical Safety and Pharmacovigilance
GSK	GlaxoSmithKline
HbsAg	Hepatitis B Surface Antigen
ICH	International Conference on Harmonisation
ICS	Inhaled Corticosteroids
IDSL	Integrated Data Standards Library
IG	Implementation Guide
IM	Intramuscular
IP	Investigational Product
IPDISC	Investigational Product Discontinuation
IRT	Interactive Response Technology
ITT	Intent-To-Treat
IV	Intravenous

Abbreviation	Description
LFT	Liver Function Test
LLQ	Lower Limit of Quantification
MMRM	Mixed Model Repeated Measures
MedDRA	Medical Dictionary for Regulatory Activities
mg	Milligram
NAb	Neutralising Antibody
OCS	Oral Corticosteroids
PCI	Potential Clinical Importance
PD	Pharmacodynamic
PDMP	Protocol Deviation Management Plan
PP	Per Protocol
PT	Preferred Term
QC	Quality Control
QTcF	Frederica's QT Interval Corrected for Heart Rate
QTcB	Bazett's QT Interval Corrected for Heart Rate
RAMOS NG	Randomization & Medication Ordering System Next Generation
RAP	Reporting and Analysis Plan
RTF	Rich Text File
SAC	Statistical Analysis Complete
SAE	Serious Adverse Event
SAS	Statistical Analysis Software
SC	Subcutaneous
SD	Standard Deviation
SDTM	Study Data Tabulation Model
SE	Standard Error
SGRQ	St. George's Respiratory Questionnaire
SMQ	Standard MedDRA Query
SOC	System Organ Class
SRM	Study Reference Manual
TFL	Tables, Figures & Listings
TST	Therapeutic Standards Team
TSQM	Treatment Satisfaction with Medication Questionnaire
VS	Versus/against

10.12.2. Trademarks

Trademarks of the GlaxoSmithKline Group of Companies	Trademarks not owned by the GlaxoSmithKline Group of Companies
NONE	SAS Xolair

10.13. Appendix 13: List of Data Displays**10.13.1. Data Display Numbering**

The following numbering will be applied for RAP generated displays:

Section	Tables	Figures
Study Population	1.1 to 1.25	1.1
Efficacy	2.1 to 2.46	2.1 to 2.11
Safety	3.1 to 3.56	3.1 to 3.2
Section	Listings	
ICH and Other Listings	1 to 44	

10.13.1.1. Study Population Tables

Study Population: Tables					
No.	Population	IDSL / TST ID / Example Shell	Title	Programming Notes	Deliverable ^[1] [Priority]
Population Analysed					
1.1.	ASE	SP1	Summary of Study Populations	IDSL Include All Subjects Enrolled, Intention to Treat, Per Protocol	SAC
Subject Disposition					
1.2.	ASE	ES6	Summary of Reasons for Screening and/or Run-In Failures	Journal Requirements	SAC
1.3.	ASE	IE2	Summary of Failed Inclusion/Exclusion/Continuation Criteria for Screening or Run-in Failures		SAC
1.4.	ASE	IE2	Summary of Failed Inclusion/Exclusion/Continuation Criteria for Subjects within the Intent to Treat Population		SAC
1.5.	ITT	NS1/SHELL	Summary of Number of Subjects by Region, Country and Centre	Add in a column for region, add a total for regions and a total for country EudraCT	SAC
1.6.	ITT	ES1	Summary of Subject Disposition	ICH E3, GSK CTR, FDAAA, EudraCT	SAC
1.7.	ITT	SD1/SHELL	Summary of Reasons for Withdrawal From Investigational Product		SAC
Demographic and Baseline Characteristics					
1.8.	ITT	DM1	Summary of Demographic Characteristics	ICH E3, GSK CTR, FDAAA, EudraCT	SAC
1.9.	ASE	DM11	Summary of Age Ranges	EMA, keep row $\geq 12-17$, $\geq 18-64$, $\geq 65-84$, ≥ 85	SAC
1.10.	ITT	DM5	Summary of Race and Racial Combinations	ICH E3, FDA, GSK CTR, FDAAA, EudraCT	SAC
1.11.	ITT	DM6	Summary of Race and Racial Combination Details	ICH E3, FDA	SAC

Study Population: Tables					
No.	Population	IDSL / TST ID / Example Shell	Title	Programming Notes	Deliverable ^[1] [Priority]
1.12.	ITT	SHELL	Summary of Asthma History and Baseline Disease Characteristics	Include GERD, CCI, mMRC	SAC
1.13.	ITT	SHELL	Summary of Previous Exacerbation History		SAC
1.14.	ITT	SU1/SHELL	Summary of History of Tobacco Use		SAC
1.15.	ITT	SHELL	Summary of Screening and Baseline Lung Function Tests	Include FEV1, FVC, FEV/FVC, %Predicted, Reversibility	SAC
Medical Conditions					
1.16.	ITT	MH4	Summary of Past Medical Conditions	ICH E3	SAC
1.17.	ITT	MH4	Summary of Current Medical Conditions	ICH E3	SAC
1.18.	ITT	FH1	Summary of Cardiovascular Assessments – Family History	Note: Family history in women <65 years or men < 55 years (first degree relatives only). Half siblings considered first degree relatives	SAC
1.19.	ITT	FH1	Summary of Cardiovascular Assessments – Screening Questions		SAC
Prior and Concomitant Medications					
1.20.	ITT	SHELL	Summary of Use of Omalizumab Therapy Prior to Treatment		SAC

Study Population: Tables					
No.	Population	IDSL / TST ID / Example Shell	Title	Programming Notes	Deliverable ^[1] [Priority]
1.21.	ITT	CM1	Summary of Asthma Concomitant Medications Started Prior to Treatment by Respiratory Medication Class Group	ICH E3 Footnote: Includes all Asthma medications started before the first dose of investigational product. Multi-component medications displayed under the respiratory medication class of each component Programming note: Display RMC and ingredient as previous Asthma studies	SAC
1.22.	ITT	CM1	Summary of Asthma Concomitant Medications Taken During Treatment by Respiratory Medication Class Group	Footnote: Multi-component medications displayed under the respiratory medication class of each component Programming note: Display RMC and ingredient as previous Asthma studies	SAC
1.23.	ITT	CM1	Summary of Asthma Concomitant Medications Taken Post-Treatment by Respiratory Medication Class Group	Footnote: Multi-component medications displayed under the respiratory medication class of each component Programming note: Display RMC and ingredient as previous Asthma studies	SAC
1.24.	ITT	CM1	Summary of Non-Asthma Medications Taken During Treatment	Footnote: Medications may be displayed under more than one ATC classification	SAC
Protocol Deviation					
1.25.	ITT	DV1B	Summary of Protocol Deviations	ICH E3	SAC

10.13.1.2. Study Population Figures

Study Population: Figures					
No.	Population	IDSL / TST ID / Example Shell	Title	Programming Notes	Deliverable [Priority]
Subject Disposition					
1.1	ITT	SHELL	Time to Subject Withdrawal From Investigation Product	See Study Population Table 1.1 (MEA117113 'final' reporting effort), but exclude 'Placebo' and Mepo 300mg SC	SAC

10.13.1.3. Efficacy Tables

Efficacy: Tables					
No.	Population	IDSL / TST ID / Example Shell	Title	Programming Notes	Deliverable [Priority]
Asthma Control Questionnaire (ACQ-5) Endpoints					
2.1.	ITT	SHELL	Summary of Asthma Control Questionnaire (ACQ-5) Score	See Efficacy Table 2.34 (MID200862 'final' reporting effort), but exclude 'Placebo' column Include screening visit in addition to baseline and post-baseline visits	SAC
2.2.	ITT	SHELL	Analysis of Change from Baseline in Asthma Control Questionnaire (ACQ-5) Score Mixed Model Repeated Measures		SAC
2.3.	PP	SHELL	Sensitivity Analysis of Asthma Control Questionnaire (ACQ-5) Score Responders: Subjects With At Least 0.5-point Improvement from Baseline (Per Protocol Population only)		SAC
2.4.	ITT	SHELL	Analysis of Change from Baseline in Asthma Control Questionnaire (ACQ-5) by number of exacerbations in previous year		SAC
2.5.	ITT	SHELL	Analysis of Change from Baseline in Asthma Control Questionnaire (ACQ-5) by baseline blood eosinophils		SAC
2.6.	ITT	SHELL	Summary of Asthma Control Questionnaire (ACQ-5) Score Responders: Subjects With At Least 0.5-point Improvement from Baseline	See Efficacy Table 2.41 (MID200862 'final' reporting effort), but exclude 'Placebo' column, and rename 'Odd Ratio to Historical Placebo'	SAC
St. George's Respiratory Questionnaire (SGRQ) Endpoints					
2.7.	ITT	SHELL	Summary of St George's Respiratory Questionnaire (SGRQ) Total Score	See Efficacy Table 2.01 (MID200862 'final' reporting effort), but exclude 'Placebo' column	SAC

Efficacy: Tables					
No.	Population	IDSL / TST ID / Example Shell	Title	Programming Notes	Deliverable [Priority]
2.8.	ITT	SHELL	Analysis of Change from Baseline in St George's Respiratory Questionnaire (SGRQ) Total Score Mixed Model Repeated Measures		SAC
2.9.	ITT	SHELL	Summary of St. George's Respiratory Questionnaire (SGRQ) Symptom Domain Score		SAC
2.10.	ITT	SHELL	Analysis of Change From Baseline in St. George's Respiratory Questionnaire (SGRQ) Symptom Domain Score		SAC
2.11.	ITT	SHELL	Summary of St. George's Respiratory Questionnaire (SGRQ) Activity Domain Score		SAC
2.12.	ITT	SHELL	Analysis of Change From Baseline in St. George's Respiratory Questionnaire (SGRQ) Activity Domain Score		SAC
2.13.	ITT	SHELL	Summary of St. George's Respiratory Questionnaire (SGRQ) Impacts Domain Score		SAC
2.14.	ITT	SHELL	Analysis of Change From Baseline in St. George's Respiratory Questionnaire (SGRQ) Impacts Domain Score		SAC
2.15.	ITT	SHELL	Summary of St George's Respiratory Questionnaire (SGRQ) Responders: Subjects With At Least 4-point Improvement in Total Score from Baseline	See Efficacy Table 2.24 (MID200862 'final' reporting effort), but exclude 'Placebo' column, and rename 'Odd Ratio to Historical Placebo'	SAC
Exacerbations					
2.16.	ITT	SHELL	Overview of Exacerbations	See Efficacy Table 2.61 (MID200862 'final' reporting effort), but exclude 'Placebo' column	SAC

Efficacy: Tables					
No.	Population	IDSL / TST ID / Example Shell	Title	Programming Notes	Deliverable [Priority]
2.17.	ITT	SHELL	Summary of Frequency of Clinically Significant Exacerbations	See Efficacy Table 2.62 (MID200862 'final' reporting effort), but exclude 'Placebo' column	SAC
2.18.	ITT	SHELL	Annualised Rate of Clinically Significant Exacerbations		SAC
2.19.	ITT	SHELL	Analysis of Time to First Clinically Significant Exacerbation	See Efficacy Table 2.68 (MID200862 'final' reporting effort), but exclude 'Placebo' column and Hazard Ration Analysis	SAC
2.20.	ITT	SHELL	Sensitivity Analysis of Annualised Rate of Clinically Significant Exacerbations (on-treatment data only)		SAC
2.21.	ITT	SHELL	Sensitivity Analysis of Annualised Rate of Clinically Significant Exacerbations (Patients with at least 12 months of prior omalizumab use)		SAC
2.22.	ITT	SHELL	Summary of Frequency of Exacerbations Requiring Hospitalisation or Emergency Department visits	See Efficacy Table 2.64 (MID200862 'final' reporting effort), but exclude 'Placebo' column	SAC
2.23.	ITT	SHELL	Annualised Rate of Exacerbations Requiring Hospitalisation or Emergency Department visits		SAC
2.24.	ITT	SHELL	Sensitivity Analysis of Annualised Rate of Exacerbations Requiring Hospitalisation or Emergency Department visits (on-treatment data only)		SAC
2.25.	ITT	SHELL	Summary of Frequency of Exacerbations Requiring Hospitalisation	See Efficacy Table 2.66 (MID200862 'final' reporting effort), but exclude 'Placebo' column	SAC
2.26.	ITT	SHELL	Annualised Rate of Exacerbations Requiring Hospitalisation		SAC
Blood Eosinophils					

Efficacy: Tables					
No.	Population	IDSL / TST ID / Example Shell	Title	Programming Notes	Deliverable [Priority]
2.27.	ITT	SHELL	Summary of Blood Eosinophils (10 ⁹ /L)	See Efficacy Table 2.73 (MID200862 'final' reporting effort), but exclude 'Placebo' column	SAC
2.28.	ITT	SHELL	Analysis of Change from Baseline in Blood Eosinophils (10 ⁹ /L)		SAC
2.29.	ITT	SHELL	Analysis of Change from Baseline in Blood Eosinophils (10 ⁹ /L) (on-treatment data only)		SAC
Pre – Bronchodilator and Post – Bronchodilator FEV1					
2.30.	ITT	SHELL	Summary of Clinic Pre-Bronchodilator FEV1 (mL)	See Efficacy Table 2.27 (MID200862 'final' reporting effort), but exclude 'Placebo' column	SAC
2.31.	ITT	SHELL	Analysis of Change From Baseline in Clinic Pre-Bronchodilator FEV1 (mL)	See Efficacy Table 2.28 (MID200862 'final' reporting effort), but exclude 'Placebo' column and Difference Analysis	SAC
2.32.	ITT	SHELL	Summary of Clinic Post-Bronchodilator FEV1 (mL)	See Efficacy Table 2.49 (MID200862 'final' reporting effort), but exclude 'Placebo' column	SAC
2.33.	ITT	SHELL	Analysis of Change From Baseline in Clinic Post-Bronchodilator FEV1 (mL)	See Efficacy Table 2.68 (MID200862 'final' reporting effort), but exclude 'Placebo' column and Difference Analysis	SAC
Response to Therapy					
2.34.	ITT	SHELL	Summary of Subject Rated Overall Evaluation of Response to Therapy (on-treatment data only)	See Efficacy Table 2.47 (MID200862 'final' reporting effort), but exclude 'Placebo' column and Odds Ratio Analysis	SAC

Efficacy: Tables					
No.	Population	IDSL / TST ID / Example Shell	Title	Programming Notes	Deliverable [Priority]
2.35.	ITT	SHELL	Summary of Clinician Rated Overall Evaluation of Response to Therapy (on-treatment data only)		SAC
Treatment Satisfaction Questionnaire for Medication (TSQM-9)					
2.36.	ITT	SHELL	Summary of Treatment Satisfaction Questionnaire for Medication (TSQM - 9) (on-treatment data only)	Summarise the Effectiveness, Convenience and Overall Satisfaction scales separately	SAC
Biomarkers					
2.37.	ITT	SHELL	Summary of CCL13 (on-treatment data only)		SAC
2.38.	ITT	SHELL	Summary of CCL17 (on-treatment data only)		SAC
2.39.	ITT	SHELL	Summary of ECP (on-treatment data only)		SAC
2.40.	ITT	SHELL	Summary of EDN (on-treatment data only)		SAC
2.41.	ITT	SHELL	Summary of Eotaxin1 (on-treatment data only)		SAC
2.42.	ITT	SHELL	Summary of Total IL-5 (on-treatment data only)		SAC
2.43.	ITT	SHELL	Summary of IL-13 (on-treatment data only)		SAC
2.44.	ITT	SHELL	Summary of MDC (on-treatment data only)		SAC
2.45.	ITT	SHELL	Summary of Periostin (on-treatment data only)		SAC
2.46.	ITT	SHELL	Summary of TSLP (on-treatment data only)		SAC

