7. PRIMARY STATISTICAL ANALYSES

7.1. Efficacy Analyses

7.1.1. Overview of Planned Efficacy Analyses

The primary efficacy analyses will be based on the Intent-To-Treat (ITT) population. Additional sensitivity analysis will be performed on the Per Protocol population.

Table 4 provides an overview of the planned efficacy analyses, with full details of data displays being presented in [Appendix 13: List of Data Displays](#).

Table 4 Overview of Planned Efficacy Analyses

Endpoint	Absolute ^[1]								Change from Baseline ^[1]							
	Stats Analysis			Summary		Individual			Stats Analysis			Summary		Individual		
	T	F	L	T	F	F	L	T	F	L	T	F	F	L	T	F
Primary Endpoint																
Asthma Control Questionnaire (ACQ-5)																
On-treatment & Off-treatment ^{[2] [3]}	Y ^[4]				Y				Y ^[4]	Y ^[5]		Y	Y		Y	

NOTES :

- T = Table, F = Figure, L = Listing, Y = Yes display generated.
- Stats Analysis = Represents TFL related to any formal statistical analyses (i.e. modelling) conducted.
- Summary = Represents TFL related to any summaries (i.e. descriptive statistics) of the observed raw data.
- Individual = Represents FL related to any displays of individual subject observed raw data.

1. Absolute and change from baseline summaries combined into a single display.
2. To be generated for Intent-To-Treat (ITT) population and Per-Protocol (PP) population.
3. Subgroup analyses to be repeated for Intent-To-Treat (ITT) population and all subgroups listed within Section [10.10.2](#).
4. Table to include both Least Square Means and Least Square Mean Changes and estimated treatment difference (Mepolizumab-Historical Placebo) and 95% confidence interval at each visit from Mixed Model Repeated Measures (MMRM) Analysis.
5. Figure to present Least Square Mean Changes and corresponding 95% confidence intervals at each visit from MMRM Analysis

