7.1.3. Analysis Comparing Against A Historical Placebo Effect

We will perform two separate analyses of the primary endpoint comparing to a historical 'placebo effect'.

[figure not shown]
Firstly, as specified in the protocol, a meta-analysis of previous exacerbation double-blind studies, MEA112997 and MEA115588, gave an estimate of -0.55 (SE: 0.05), for the improvement in the ACQ-5 score for placebo subjects at Week 32 compared to baseline. The observed improvement in this study for following mepolizumab treatment will be compared to this historical improvement on placebo.

Secondly, a meta-analysis has been performed of subjects within studies MEA115588 and 200862 who reported previous Xolair use, which may represent a more comparable population for this study. Study 200862 has completed since the protocol was finalised and previous Xolair usage was not collected in study MEA112997.

At Week 32 an estimate of -0.29 (SE: 0.248) was reported in the MEA115588 study while at Week 24 study 200862 reported an estimate of -0.03 (SE: 0.164) for the improvement in the ACQ-5 score for placebo subjects who previously used Xolair.

Weighted meta-analysis was performed on these values to get the combined estimate of -0.11 (SE: 0.14) for the historical placebo effect (Figure 1). This shows a reduction in the ACQ-5 score, but not as large as that specified in the protocol. The observed improvement in this study for mepolizumab vs. baseline will be also compared to this historical improvement on placebo.

Figure 1 Meta-analysis of ACQ-5 Placebo Effect in Previous Xolair Users

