Model Results Presentation

 Adjusted means and the corresponding 95% confidence intervals will be presented by visit. Plots of LS means ratio to baseline in blood eosinophil count and 95% confidence intervals from the model will be generated by visit.
On-treatment Phase

 All subjects in the ITT population will be included within this analysis. All data collected up to and including Week 32 from patients, including those who have discontinued study treatment, will be included in the analysis. An On-Treatment “de jure” analysis will also be performed which does not consider any data collected following treatment discontinuation (see On-Treatment definition within Section 10.4).

Other Statistical Analyses
Other Endpoint

 Percentage of subjects achieving a 0.5-point or greater reduction from baseline in ACQ-5 score at Week 32
Results Presentation

 The number and percentage of subjects achieving a 0.5-point or greater reduction in ACQ-5 Score compared to baseline will be presented for each visit. The number of subjects with a missing ACQ-5 Score at each visit will be presented in a separate category.

On-treatment Phase
• See Primary Efficacy Statistical Analysis, Section 7.1.2

Other Statistical Analyses
Other Endpoint
• Percentage of subjects achieving a 4-point or greater reduction from baseline in SGRQ score at Week 32
Results Presentation

 The number and percentage of subjects achieving a 4-point or greater reduction in SGRQ Total score compared to baseline will be presented for each visit. The number of subjects with a missing SGRQ Total Score at each visit will be presented in a separate category.
On-treatment Phase
• See Primary Efficacy Statistical Analysis, Section 7.1.2

Other Statistical Analyses
Other Endpoint
• Mean change from baseline in pre- and post- bronchodilator FEV1 at Week 32
Model Specification
• See Primary Efficacy Statistical Analysis, Section 7.1.2
Model Checking & Diagnostics
• Refer to Appendix 11: Model Checking and Diagnostics for Statistical Analyses .
Model Results Presentation

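### Two responder tables carry an odds ratio to historical placebo that the SAP analysis sections do not plan and for which neither document gives a comparator

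*SAP*

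**What the plan says.** The notes for Tables 2.6 and 2.15 in SAP 10.13.1.3 each point to a table from study 200862 (its Tables 2.41 and 2.24) and give the same instruction: "exclude 'Placebo' column, and rename 'Odd Ratio to Historical Placebo". The item at issue is thus labelled "Odd Ratio to Historical Placebo" in both. Both tables are listed as deliverables.

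The analysis sections describe something narrower. For ACQ-5 responders, SAP 8.1.2 states: "The number and percentage of subjects achieving a 0.5-point or greater reduction in ACQ-5 Score compared to baseline will be presented for each visit". For SGRQ it plans "The number and percentage of subjects achieving a 4-point or greater reduction in SGRQ Total score compared to baseline", again by visit. In both cases missing scores form a separate category. Neither entry has a model specification, a test or an odds ratio. Appendix 11, which lists the endpoints analysed by model, includes no responder endpoint.

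The historical comparison is set out in SAP 7.1.3: "We will perform two separate analyses of the primary endpoint comparing to a historical" placebo effect. The benchmarks are mean ACQ-5 changes of -0.55 (SE 0.05) and -0.11 (SE 0.14). In SAP Table 4 the planned contrast is an "estimated treatment difference (Mepolizumab-Historical Placebo"), a difference in means. Protocol 9.4.3.1 leaves the analysis of the other efficacy endpoints to the RAP.

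**The concern.** An odds ratio needs a control proportion. This trial has no control arm, and the plan names no historical proportion, source study, population, visit, missing-data rule or interval method from which to build one. For SGRQ there is not even a historical mean.

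The item does not read like harmless leftover text. Where other 200862 tables were adapted, the between-arm contrast was removed in so many words. The note for Table 2.19 drops the hazard ratio, those for Tables 2.31 and 2.33 drop the difference analysis, and that for Table 2.34 says "exclude 'Placebo' column and Odds Ratio Analysis". In the two responder tables the contrast is relabelled instead. Someone programming from the list could reasonably produce it and would have to find a control.

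In an open-label single-arm trial that choice could be made with the trial's own responder rate in view, and the study report would then contain an effect estimate that no analysis section planned.

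**Working it through.** **1. The plan's own historical figures reproduce, but all are means.**

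- Inputs from Protocol 9.2.1: 120 treated, 15% withdrawal, residual SD 0.96, placebo effect -0.55, true change -0.86, two-sided 5%.
- n = 120 × 0.85 = 102; SE = 0.96/√102 = 0.0951.
- Change needed for significance = -0.55 - 1.96 × 0.0951 = -0.736 (stated: -0.74).
- Power = Φ(0.31/0.0951 - 1.96) = Φ(1.30) = 90.3% (stated: 90%).
- Previous-Xolair benchmark (SAP 7.1.3), inverse-variance pooling of -0.29 (SE 0.248) and -0.03 (SE 0.164): weights 16.26 and 37.18; pooled mean = (-4.715 - 1.115)/53.44 = -0.109; SE = 1/√53.44 = 0.137 (stated: -0.11, SE 0.14).

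None of these is a responder proportion, so none supplies the denominator of an odds ratio.

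**2. The relevant parts of the SAP side by side.**

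| Place | Responder endpoints |
|---|---|
| 8.1.2 | Number, percentage, missing category |
| Appendix 11 | Not among the modelled endpoints |
| 7.1.3 | Historical comparison for the primary endpoint only, as mean ACQ-5 changes |
| Notes to Tables 2.6 and 2.15 | Odds ratio to historical placebo |

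**3. How much the missing comparator could matter (illustration only).** Assume that changes are normally distributed, that the SD is the protocol's 0.96 in every group, and that someone converts a benchmark mean into a responder rate. The documents propose no such conversion.

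- Responder rate = Φ((-0.5 - mean)/SD).
- Benchmark -0.55: Φ(0.05/0.96) = 52.1%; odds 1.09.
- Benchmark -0.11: Φ(-0.39/0.96) = 34.2%; odds 0.52.
- Mepolizumab at -0.86: Φ(0.36/0.96) = 64.6%; odds 1.83.
- Odds ratio = 1.83/1.09 = 1.68, or 1.83/0.52 = 3.51, a 2.1-fold spread.

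Over a range of assumed SDs:

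| SD | Rate at -0.55 | Rate at -0.11 | Rate at -0.86 | OR against -0.55 | OR against -0.11 |
|---|---|---|---|---|---|
| 0.85 | 52.3% | 32.3% | 66.4% | 1.80 | 4.14 |
| 0.96 | 52.1% | 34.2% | 64.6% | 1.68 | 3.51 |
| 1.05 | 51.9% | 35.5% | 63.4% | 1.61 | 3.15 |
| 1.20 | 51.7% | 37.3% | 61.8% | 1.51 | 2.72 |

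**4. Handling of missing scores.** With 102 of 120 observed and 64.6% responding, there are about 66 responders. Excluding missing scores gives odds of 66/36 = 1.83; counting them as non-responders gives 66/54 = 1.22. The factor is 54/36 = 1.5. The separate missing category in 8.1.2 works for a percentage table but does not say which odds to use.

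**5. SGRQ.** With no historical SGRQ value in either document, no comparable range can be derived.

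**The case against.** The strongest reply is that every planning section treats these endpoints as descriptive. The two table titles begin with the word Summary, 8.1.2 gives a presentation and no model, and 7.1.3 confines the historical comparison to the primary endpoint. The note is also garbled, since its verb has no clear object, and the shells sit in separate documents (Appendix 14) that may define the item or drop it. The SAP adds that decisions on its analyses will be made before database freeze.

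Much of this stands. It shows that the odds ratio could be produced, not that it will be. It does not remove the inconsistency: the other display notes show that the sponsor deleted such contrasts when it meant to, and a comparator should not be left to a shell. A decision before freeze is also not necessarily a decision before results can be seen, because the trial is open-label with one arm and the freeze follows the last exit visit.

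Two stronger readings are tempting:

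- A reader might infer that no historical responder rate exists. The documents do not show that. The 200862 source tables had a placebo column, so figures probably exist in the sponsor's files. What can be said is that the SAP does not adopt them. It cites 200862 for ACQ-5 at Week 24, while the endpoint here is Week 32.
- A reader might infer that the 7.1.3 benchmarks should be confined to the overall ITT analysis. That conflicts with SAP Table 4, whose notes 2 to 4 plan the ACQ-5 output for the ITT and PP populations, repeat it for subgroups and include the historical difference. Nothing in the responder notes is an argument against that.

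**Conclusion.** The point holds as an internal inconsistency in the SAP. Two display notes carry an inferential contrast that the analysis sections do not plan, and neither document gives or designates its comparator.

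For ACQ-5 the choice between the SAP's own two benchmarks would move the odds ratio from about 1.7 to about 3.5. That rests on normal changes, a common SD of 0.96, a mean change of -0.86 and conversion of means into rates. These are assumptions made to show scale, not a prediction. The odds ratio also depends on this trial's own responder rate and on how missing scores are counted. For SGRQ the size cannot be stated.

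The consequences are limited. Both are Other endpoints, and the primary and secondary analyses are untouched. The conclusion could change if the shells, which were not available, already define or omit the item.

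**What to change.** Change the notes for Tables 2.6 and 2.15 so that they exclude both the placebo column and the odds ratio analysis, in line with the note for Table 2.34. Report the number and percentage of responders with the missing category, as 8.1.2 plans. A confidence interval for the percentage would be a sensible optional addition, but 8.1.2 does not describe one. Leave the historical comparison of the mean ACQ-5 change in Table 4 as it is.

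The cost is two programming notes, plus the matching shells if they carry the row. No new data are needed.

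If the sponsor does want the contrast, it would have to specify before database freeze the source studies, population, visit, responder counts, missing-data rule and an interval that carries the uncertainty of the historical rate. That is considerably more work for two Other endpoints.
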